1.6.6. CLINICAL EXPERIENCE CONCLUSIONS

Data collected to date data support the feasibility and safety of intramuscular injections of VM202 in subjects with critical limb ischemia and DPN. Results suggest that this therapeutic approach may improve functional outcomes and provide symptomatic relief. VM202 is rapidly eliminated from circulation, and appears to remain active only at the injection site. The incidence of complications did not appear to be significantly different between treatment cohorts. Continued study of VM202 in subjects with CLI and DPN is warranted.

1.7. STUDY AND DOSE RATIONALE

Diabetic peripheral neuropathy, by definition, is a bilateral neuropathy. Treating only one leg may confound patient-reported pain levels and quality of life measures. Based on the excellent safety profile of VM202 observed in the phase I and phase II CLI studies and the safety and preliminary efficacy data from the phase I/II studies of VM202 injections in subjects with DPN, we propose continued bilateral treatment in this phase III study.

One dose of VM202 will be tested against placebo (VM202 vehicle). The total dose of VM202 per leg will remain within the dosing scheme of the phase II study (mg / leg, for a total of mg / subject). However, instead of two treatments of intramuscular injections in the calf (on Day 0 and Day 14), as performed in the prior DPN studies, subjects will receive VM202 or placebo (VM202 vehicle) by intramuscular injections in both legs (in the calf) on Day 0, and Day 14, followed by a second treatment on Day 90 and Day 104. Studies have shown that copies of VM202 in whole blood were greatly reduced or completely negative within one week after final VM202 dosing (Day 21). Serum HGF levels remained relatively constant throughout the study. The phase II DPN study showed greater improvements at 3 months than 6 months indicating that the effects of VM202 attenuate over time justifying a second treatment in the current study.

As in all prior/ongoing studies, VM202 will be delivered in a solution of VM202 / mL. Subjects will be treated with an overall final dose of mg VM202 or placebo, dosages well within those supported by the body of pharmacology and toxicology safety studies of VM202. No toxicities were reported in the phase II DPN study. Safety studies in rabbit, rat and mouse models demonstrate that doses approximately $2\frac{1}{2}$ (mg/kg) to 30 (mg/ kg) times the clinical dose (mg) proposed in this study are safe and resulted in no toxicities.

2. GOOD CLINICAL PRACTICES (GCP) STATEMENT

This trial will be conducted in compliance with all applicable federal regulations pertaining to investigational drugs and devices including but not limited to: 21 CFR Part 50, Part 54, Part 56, Part 312, and GCP standards. This trial will be conducted in compliance with the protocol as approved by an Institutional Review Board (IRB) and an Institutional Biosafety Committee (IBC). Any deviations from the protocol that may affect the safety and welfare of study participants will be immediately reported to the Sponsor and to the IRB and IBC per each institution's guidelines.

3. INVESTIGATIONAL PLAN

3.1. STUDY OBJECTIVES

The objective of this Phase III study is to evaluate the safety and efficacy of IM administration of VM202 in subjects with painful DPN in lower extremities.

3.2. STUDY DESIGN

This is a phase III, double-blind, randomized, placebo-controlled, multicenter, 9-month study designed to assess the safety and efficacy of VM202 in subjects with painful DPN. Subjects with painful DPN will be screened for study eligibility after giving informed consent.

Initial Screening Activities. Prior to screening, subjects will provide informed consent and then be initially screened using the VAS, the symptoms portion of the BPNS and the MNSI. Only subjects with a VAS score of ≥ 40 mm, a ≤ 5 -point difference in symptom of BPNS between legs and MNSI score of ≥ 3 will be allowed to proceed with the full screening procedures.

Screening. If the VAS, BPNS and MNSI criteria are met, the rest of screening will proceed. If applicable, the subject will be washed out of prohibited medications. During medication wash-out, screening procedures consisting of assessment of study eligibility, a complete medical history, vital signs, physical exam, concomitant medications, cancer screening tests, viral screening, 12 lead EKG, retinal fundoscopy, serum chemistry, hematology, including HbA1c, and urine pregnancy test (women of childbearing potential only) may occur.

If applicable, the subject will be washed out of prohibited medications 14 days prior to initiation of the 7-day Daily Pain and Sleep Interference Diary. The Daily Pain and Sleep Interference Diary must be completed within 14 days of the first injections. Subjects will be asked to rate their 24-hour average daily pain intensity score using an 11-point numerical scale with 0 = no pain - 10 = worst pain possible, and to evaluate how much their pain interferes with sleep (also an 11 point numerical rating scale from 0 (did not interfere with sleep) to 10 (completely interfered with sleep; subject was not able to sleep due to pain). The subject must record at least five assessments of the 24-hour average daily pain intensity score during the sevenday period. The mean baseline 24-hour will represent the baseline reference value. The average daily pain intensity score of the Daily Pain and Sleep Interference Diary must be ≥ 4 with a standard deviation ≤ 2 in order to be eligible for study participation.

Data from the Daily Pain and Sleep Interference Diary at screening and BPI-DPN on Day 0 will represent the baseline reference values.

All screening assessments should occur within the 90 days prior to Day 0 (day of first injections), and the diary must be completed within 14 days prior to Day 0.

Randomization. Subjects who meet the eligibility criteria will be randomly assigned in a 2:1 fashion to one of the two treatment arms: VM202 (32 mg VM202 total dose, 16 mg / leg), or placebo, respectively. Randomization will be stratified by current use of gabapentin and/or pregabalin. Assignment to a treatment arm will be centralized, using an independent predetermined randomization scheme in a double-blinded fashion. Blinding will be achieved by having the study medication (VM202 and placebo [VM202 vehicle]) prepared by the study pharmacist. Reconstituted VM202 is indistinguishable from the VM202 vehicle.

First Treatment. Prior to the first injection, vital signs, concomitant medications, VAS, BPI-DPN, Semmes-Weinstein monofilament testing, and nerve conduction (only at select sites), testing will be conducted. In addition, blood will be drawn for determination of serum chemistry and hematology, HbA1c, serum HGF, and copies of VM202.

Subjects will receive VM202 or placebo (VM202 vehicle) by intramuscular injections in both legs (in the calf) on Day 0, and Day 14 as follows:

Table 2. First Treatment: Day 0 and 14

TREATMENT GROUP	DOSE VM202 (mg)/Visit/Leg	FINAL DOSE	FINAL DOSE VM202 / SUBJECT / TREATMENT (mg)	
	DAY 0	DAY 14	VM202 / LEG (mg)		
VM202 Placebo	4 0	4 0	8 0	16 0	

0 = injections of VM202 vehicle

All subjects will receive sixteen (16) 0.5 mL injections evenly distributed over each calf at each visit of VM202 or placebo.

Subjects randomized to the VM202 treatment arm will receive the following intramuscular injections in each calf:

- Day 0 16 injections of 0.5mL of VM202 / calf
- Day 14 16 injections of 0.5mL of VM202 / calf

Subjects randomized to the placebo control group will receive the following intramuscular injections in each calf:

- Day 0 16 injections of 0.5mL of VM202 vehicle / calf
- Day 14 16 injections of 0.5mL of VM202 vehicle / calf

Note: Visually, VM202 vehicle is indistinguishable from reconstituted VM202. The subject and clinician will not be able to distinguish placebo from VM202 injections.

1 to 3 hours post injection on Day 0 and Day 14, vital signs, and blood draw for determination of copies of VM202 will be performed, and the occurrence of injection site reactions and adverse events will be assessed.

Subjects will be assessed at Day 21 and Day 60; at both visits, vital signs, and concomitant medications will be determined. Blood will be drawn for determination of serum HGF, and copies of VM202. The occurrence of injection site reactions and adverse events will be assessed.

Within 14 days of the Day 90 visit, the Daily Pain and Sleep Interference Diary will be completed.

Second Treatment. Prior to the second treatment on Day 90, vital signs, concomitant medications, VAS, BPI-DPN, PGIC, and Semmes-Weinstein monofilament testing will be conducted. Blood will be drawn for determination of serum chemistry and hematology, HbA1c, serum HGF, and copies of VM202. The occurrence of injection site reactions and adverse events will be assessed.

Subjects will receive the prior randomly assigned treatment (VM202 or placebo/VM202 vehicle) by intramuscular injections in both calves on Day 90, and Day 104 as follows:

Table 3. Second Treatment: Day 90 and 104

TREATMENT GROUP	DOSE VM202 (mg) / VISIT / LEG	FINAL DOSE	FINAL DOSE VM202 / SUBJECT / TREATMENT (mg)	
	DAY 90	DAY 104	VM202 / LEG (mg)		
VM202	4	4	8	16	
Placebo	0	0	0	0	

0 = injections of VM202 vehicle

Note, the Day 104 visit will be scheduled 14 days \pm 1 day following the Day 90 visit.

All subjects will receive sixteen (16) 0.5 mL injections evenly distributed over each calf at each visit of VM202 or placebo.

Subjects randomized to the VM202 treatment arm will receive the following intramuscular injections in each calf:

- Day 90 16 injections of 0.5mL of VM202 / calf
- Day 104 16 injections of 0.5mL of VM202 / calf

Subjects in the placebo control group will receive the following intramuscular injections in each calf:

Day 90 – 16 injections of 0.5mL of VM202 vehicle / calf

• Day 104 – 16 injections of 0.5mL of VM202 vehicle / calf

1 to 3 hours post injection on Day 90 and Day 104, vital signs, and blood draw for determination of copies of VM202 will be performed, and the occurrence of injection site reactions and adverse events will be assessed.

HGF serum levels will be determined immediately pre-treatment on Day 0, immediately pre-treatment on Day 14, on Day 21, Day 60, immediately pretreatment on Day 90, immediately pre-treatment on Day 104, Day 111, Day 150, Day 180 and Day 270.

The number of copies of VM202 in whole blood will be determined at Day 0 (preinjection, and 2 hours [± 1 hour] post injection), at Day 14 (pre-injection, and 2 hours [± 1 hour] post injection), Day 21, Day 60, at Day 90 (pre-injection, and 2 hours [\pm 1 hour] post injection), at Day 104 (pre-injection, and 2 hours [\pm 1 hour] post injection), Day 111, Day 150, Day 180 and Day 270.

Serum chemistry, hematology and HbA1c will be determined on Day 0, Day 90, Day 180, and Day 270.

VAS, BPI-DPN, and Semmes Weinstein monofilament testing will be recorded at Day 0, Day 90, Day 180, and Day 270. Patients' Global Impression of Change (PGIC) will be recorded at Day 90, Day 180 and Day 270. MNSI will be conducted at Day 180 and Day 270 to track disease progression.

The Daily Pain and Sleep Interference Diary will be completed by subjects before the Day 90, Day 180, and Day 270 visits.

Nerve conduction will be conducted on Day 0, Day 180 and Day 270 at select sites. Retinal fundoscopy will be conducted at Day 180 and Day 270. Rescue medication (i.e., Acetaminophen [Tylenol]) taken for DPN pain will be dispensed on Day 0 and use will be documented throughout the 9-month follow-up visit.

Adverse events, concomitant medications and vital signs will be recorded throughout the 9-month follow-up period, while injection site reactions will be assessed through Day 150.

A summary of the schedule of evaluations and visits can be found in Appendix 1.

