3.7. PRIOR AND CONCOMITANT MEDICATION

All concomitant medications (taken within 60 days of the first injection) will be recorded at each study visit. For each medication taken, the following information will be collected:

- Medication trade name;
- Indication for which the medication was given;
- Dose/strength, route, and frequency of administration;
- Date started and date stopped (or continuation at study exit).

EXAMINATIONS AND EVALUATIONS 4.

4.1. **EVALUATIONS CONDUCTED AT BASELINE ONLY**

MEDICAL HISTORY 4.1.1.

A complete medical history will be obtained at Baseline. All positive and negative findings will be carefully documented on the study worksheets. Any new finding discovered during the Screening/Baseline evaluation and prior to the first study drug administration (Day 0) will be considered to be part of the medical history and will not be recorded as an adverse event.

The Investigator will perform an especially detailed assessment of past diabetes history to include all events and interventions prior to study enrollment. Other potential causes of peripheral neuropathy will be excluded (e.g., alcohol consumption, renal failure, liver disease, hypothyroidism, collagen vascular diseases, vasculitis, osteoarthritis of the ankle or foot, gout, bursitis, fasciitis, and B-12 or folate deficiency).

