5.3. REPORTING/RECORDING OF AES

Throughout the course of the study, all efforts will be made by the investigator to remain alert to possible AEs. The first concern will be the safety of the subject, and for providing appropriate medical intervention. The period of observation for collection of AEs starts during the first intramuscular injection procedure (Day 0) until the 9 month follow-up visit. Any AE should be recorded on the appropriate study worksheet.

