5.4. REPORTING / RECORDING OF SAES

5.4.1. INVESTIGATOR'S RESPONSIBILITY

SAEs will be recorded following the first study drug administration through the 9-month follow-up visit. Any serious adverse event or unexpected adverse event that occurs during this investigation, whether or not related to the study medication, must be reported as soon as possible but no later than 3 working days after the investigator first learns of the event to the Sponsor and the designated CRO by completing the SAE form and the AE information in the EDC and selecting appropriate criteria that classifies the AE as serious and/or unexpected. In order to have the Investigator's signature on file, the signed SAE form needs to be uploaded to the EDC at the time of initial data entry.

Each SAE must be followed with appropriate medical management until resolved or assessed as chronic or stable regardless of whether or not, in the opinion of the Investigator, the event is thought to be related to the study medication.

The Investigator will be required to provide complete information (including the Investigator's opinion of the relationship of the SAE to the study medication) concerning each SAE to the CRO and Sponsor within 5 working days of first learning of the event. This information must be recorded in the subject's medical record and then entered into the EDC. Copies of related source documentation such as results/reports, hospitalization records, and other relevant information must be obtained if possible.

In the event of an SAE leading to hospitalization, every effort will be made by the investigational site to obtain medical records, including a hospital discharge summary. In the event of a fatal AE, documentation of any available postmortem findings, including autopsy, will be provided to the Sponsor or their designee. In any event, the Investigator will provide a narrative summary of circumstances, events related to the death, and cause of death, if known.

The Investigator must comply with the applicable local regulatory requirements related to the reporting of SAEs to regulatory authorities and the Institutional Review Board (IRB), and Institutional Biosafety Committee (IBC) if applicable. Upon receipt from the Sponsor of an initial or follow-up IND Safety Report or other

safety information, the Investigator must promptly notify his or her IRB, and IBC (if applicable).

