6.4. SUBJECT CATEGORIZATION

Screen Failure - Any subject who was consented and entered into the Screening process appropriately, but subsequently did not meet the entry criteria in order to be treated. Subjects who fail screening will not be followed for safety or efficacy assessment, and no other study procedures will be performed. Screen failures will be replaced.

Evaluable Subject - Any subject who received the study drug.

Lost to follow-up - A subject deemed to be lost to follow-up is any subject who received treatment, but who does not complete scheduled study visits. This includes those subjects who withdraw consent and refuse further study participation and all attempts to contact the subject are deemed unsuccessful.

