8.5.3. Adverse Events

All adverse event summaries will be restricted to Treatment Emergent Adverse Events (TEAE), which are defined as AEs that occur after dosing and pre-existing medical conditions that worsen following exposure to an investigational product. An AE with a missing start date and a stop date that is either missing or on or after the treatment start date will be considered as a TEAE. For summary purposes, verbatim terms reported by the study centers will be mapped to MedDRA (v21.0 or later) system organ classes (SOC) and preferred terms by the CRO and approved by the CDRC. It should be noted that only AEs that occurred after the first injection will be collected during the study.

The adverse event listings will be displayed by treatment group. The number of subjects experiencing a particular event, the percentage of subjects experiencing the event, and the total number of events will be presented. The following summaries will be created:

- TEAE by SOC and preferred term;
- TEAE by SOC, preferred term and protocol version;
- TEAE by SOC, preferred term and maximum severity. At the across-SOC and preferred term levels of subject summarization, a subject is classified according to the highest severity if the subject reported one or more events; severity within an SOC is not summarized. AEs with missing severity will be considered severe for this summary;
- TEAE by SOC, preferred term and closest relationship to study treatment (Related/Not Related). At each level of subject summarization, a subject is classified according to the closest relationship if the subject reported one or more

events. AEs with a missing relationship will be considered related for this summary; events classified as 'possibly', 'probably' or 'definitely' will be considered 'related'.

- Serious TEAEs by SOC and preferred term;
- TEAEs leading to study discontinuation by SOC and preferred term;
- Adverse events of special interest (AESI) by preferred term. Specific areas of special interest to be presented separately are for dizziness, somnolence, weight increase, peripheral edema, and falls as well as subsets of events within the Nervous System disorders, Investigations, and Injury, Poisoning and Procedural Complications system organ classes. The specific preferred terms within these subsets will be determined at the blinded data review.
- Injection Site Reactions (ISRs) included under AESI will include designations of relatedness and severity.

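### Subjects on prohibited drugs are washed out after consent, but AE and SAE recording starts only at the first injection, so harm caused by the washout or by screening is not captured as such

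*Protocol*

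**What the plan says.** **Washout.** Consent comes first, then screening, which may last up to 90 days. Within it, protocol 3.2 says: "If applicable, the subject will be washed out of prohibited medications. During medication wash-out, screening procedures consisting of assessment of study eligibility" and the remaining tests may take place. Exclusion 16, Section 3.4.5.2 and Appendix 3 list what must stop before the baseline diary: opioids, muscle relaxants, benzodiazepines apart from a stable bedtime dose, capsaicin, local anesthetic creams and patches, and some other therapies. Exclusion 20 adds regular COX inhibitors and steroids, to be washed out before first dosing.

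**Recording.** Section 4.1.1 keeps new findings at Screening or Baseline out of the AE record: any that arise "prior to the first study drug administration (Day 0) will be considered to be part of the medical history and will not be recorded". Section 5.2 asks for AEs after the first administration. In Section 5.3 the AE collection period "starts during the first intramuscular injection procedure (Day 0) until the 9 month follow-up visit". Section 5.4.1 opens: "SAEs will be recorded following the first study drug administration through the 9-month follow-up visit". SAP 8.5.3 notes that "only AEs that occurred after the first injection will be collected during the study".

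**Subjects who are never dosed.** Protocol 6.4: "Subjects who fail screening will not be followed for safety or efficacy assessment". SAP 6.2 nevertheless counts consented screen failures in the safety population and promises to summarize their safety data. Protocol 3.5.2 lists a pre-treatment AE as a possible reason for discontinuation.

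**The concern.** Stopping an opioid or an anti-inflammatory in order to enter a trial is done because the trial requires it, and so are the screening tests ordered for it. Any harm that follows comes from the protocol. Under the stated rules, a hospital admission caused by a required withdrawal would be entered as medical history. It would carry no seriousness or causality assessment, would not fall under the 3-working-day SAE report, and would not be among the reported AEs that protocol 6.3.6 and SAP 7.5 name as DSMB input. Sponsor and DSMB would then have no organized view of one risk that the design itself creates. What is at stake is safety oversight, not the efficacy result.

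**Working it through.** No sample size, power or error rate is involved. The check sets the texts side by side and counts days.

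**1. When does recording start?** Protocol 4.1.1, 5.2, 5.3 and 5.4.1 and SAP 8.5.3 give the same answer: the first injection. The AE definition in 5.1 is also tied to exposure to the product. Section 5.4.1 goes on to require reporting of serious events that occur during the investigation, which could be read more widely, but its opening sentence sets the window. At best the SAE rule is ambiguous. No text available for review sets up AE or SAE capture between consent and Day 0.

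**2. How long is a washed-out subject unobserved?** Inputs:
- Washout before the diary: 7 days (exclusion 16, 3.4.5.2, Appendix 3) or 14 days (3.2). These contradict each other.
- The diary runs 7 days and falls within the 14 days before Day 0 (3.2), so it starts 7 to 14 days before Day 0. Section 3.4.8 (Day -7, with a 7-day allowance before it) agrees.

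Time off drug before recording = washout days + days from diary start to Day 0.
- 7-day rule: 7 + 7 = 14 to 7 + 14 = 21 days.
- 14-day rule: 14 + 7 = 21 to 14 + 14 = 28 days.

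It is longer if the diary must be repeated (3.4.3). All of it falls before the first injection.

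**3. Where could such an event still leave a trace?**
- Changes in medical history are noted before injection on Day 0 (3.4.9), and SAP 8.3 summarizes medical history by MedDRA class and term in the ITT population. Nothing there separates onset after consent from older history.
- Section 3.5.2 has the reason for discontinuation recorded, and subjects discontinued for an AE followed until it resolves or is stable.
- For screen failures, 3.4.5.3 asks only for a reason on the Screening Log.

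**4. Do the documents agree with one another?** No.
- 3.5.2 names a pre-treatment AE as a discontinuation reason, although no such AE is collected.
- SAP 6.2 requires at least one injection for the safety population, then includes screen failures, who have none.
- The safety summary promised for screen failures has no AE source, because 6.4 gives them no safety follow-up.
- Seven subjects were randomized in error and withdrawn before dosing (footnotes to protocol 6.2.1 and SAP 6.1), so consented but undosed subjects exist.

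**5. Scale, as background only.** Phase II had SAEs in 10 of 103 subjects over 9 months (1.4). Assuming a constant hazard over 270 days, h = -ln(1 - 10/103)/270 = 0.000378 per day. Then 1 - exp(-14h) = 0.5% and 1 - exp(-28h) = 1.1%. This is the general SAE rate for a window of that length. It is not an estimate of harm from washout.

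**The case against.** The strongest reply is that this is a deliberate and consistent choice: an AE is defined by exposure to the product, the DSMB's remit is the safety of VM202, and endpoints, error control and TEAE rates are untouched. The consistency stands. But the choice leaves serious harm caused by the protocol outside SAE reporting, and it does not fit 3.5.2 or SAP 6.2.

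It is also fair to say that such events are not wholly invisible. Medical history, Day 0 changes and discontinuation reasons can hold them. None of these routes labels an event as serious or attributes it to the washout.

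Screening risk should not be inflated. Chest imaging may predate consent (4.1.3), and fluorescein angiography is optional (4.2.1).

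Four stronger readings are tempting and are not supported:
- **Every subject is taken off analgesics.** Washout applies only to users of prohibited drugs. A stable bedtime benzodiazepine is exempt, and gabapentin, pregabalin, duloxetine, antidepressants and other anti-epileptics are continued at a stable regimen.
- **The gap off drug is 90 days.** That is the maximum screening window, not the washout.
- **A count of missed SAEs can be given.** Applying the Phase II rate to 30–90 days and 477 subjects gives about 5–16. That rate is background: all those SAEs were classed as unrelated to study drug or placebo (1.6.4), and nothing ties them to washout. Also, 477 is the number randomized, and neither the number consented nor the share washed out is stated.
- **The baseline is biased.** Baseline pain is deliberately measured after washout and before randomization, so the washout cannot depend on the assigned arm. Prior conditions that worsen after dosing still count as TEAEs.

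**Conclusion.** The gap is real and rests on explicit text. For subjects who must stop a prohibited analgesic, about 14–21 or 21–28 days off drug pass with no AE or SAE recording, depending on which of two contradictory washout rules applies. These figures assume that the whole diary lies within the 14 days before Day 0 and is not repeated. An SAE caused by the washout or a screening procedure in that time is neither classified nor reported as one, and does not reach the DSMB as a reported AE. How many such events would occur cannot be derived from the documents.

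This is an inexpensive improvement in participant protection. It does not threaten the primary analysis. The consent form and part of Appendix 3 were removed before review and the DSMB Charter was not supplied, so nothing is concluded from their absence.

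**What to change.** - **Protocol 4.1.1, 5.2, 5.3, 5.4.1:** record SAEs from signed consent. Between consent and first injection, also record AEs judged related to protocol-required washout or a screening procedure, including in screen failures. Word the 5.1 definition so that these pre-treatment events are covered.
- **SAP 8.5.3:** amend the sentence limiting collection to post-injection AEs, and add one pre-treatment listing that also goes to the DSMB. Flag these events explicitly. Otherwise the rules for missing start dates (SAP 8.5.3) and partial start dates (SAP 7.7.2, Table 4) could move some of them into the TEAE tables, which should stay unchanged.
- **Reconcile** protocol 3.5.2, protocol 6.4 and SAP 6.2 on pre-treatment AEs and screen failures, and the 7-day and 14-day washout statements.
- **Subjects already enrolled:** list medical-history entries with onset between consent and Day 0, and state the limitation in the CSR.

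**Cost:** wording changes, a little data entry and one listing. No visit, procedure or sample size changes. Retrospective capture will be incomplete: SAP Section 3 puts 62 + about 278 = about 340 subjects as randomized before version E was implemented.
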